We will conduct a rigorous 12-week randomized controlled trial in which 160 women with overactive bladder (OAB) syndrome will be assigned to: 1) use a standard guided-breathing device to slow their respiratory rate to 5 to 10 BPM for at least 15 minutes per day at home, or 2) use an identical-appearing control device that does not guide their breathing but plays relaxing, non-rhythmic music while monitoring their spontaneous breathing pattern. Our aims are:

Aim 1: To determine whether a device-guided slow-breathing exercise program can reduce the frequency and severity of OAB symptoms in women.

Compared to controls, we hypothesize that women randomized to practice slow breathing for at least 15 minutes per day for 12 weeks will report a more than 20% greater reduction in frequency of any voiding or incontinence episodes associated with moderate or severe urgency (measured by a validated voiding diary), in addition to greater improvements in frequency of other OAB symptoms and quality-of-life impact of OAB symptoms (measured by diary or by questionnaire).

Aim 2: To determine whether this slow-breathing intervention can improve autonomic nervous system control in women with OAB, and explore change in autonomic control as a mechanism of treatment effects on OAB symptoms.

Compared to controls, we hypothesize that women randomized to practice slow-breathing will demonstrate significantly improved autonomic control as measured by high-frequency heart rate variability and pre-ejection period parameters, and that treatment effects on OAB symptoms will be at least partly mediated by improvements in autonomic control.

Aim 3: To determine whether this slow-breathing intervention can improve anxiety-related symptoms in women with OAB, and explore changes in anxiety as a mediator of treatment effects on OAB symptoms.

Compared to controls, we hypothesize that women with OAB randomized to practice slow-breathing exercises will report significant improvement in anxiety-related symptoms (as measured by validated questionnaires), and that treatment effects on OAB symptoms will be at least partly mediated by improvement in anxiety.

C. BACKGROUND & JUSTIFICATION

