We propose to conduct a rigorous, 12-week, randomized controlled trial of a device-guided slow-breathing exercise program in 160 ambulatory women who report an average of at least 3 urgency-associated voiding or incontinence episodes per day, do not have a history of urinary tract surgery, cancer, irradiation, or major neurologic disease, and are not receiving other medical treatments for OAB. Participants will be randomized in a 1:1 ratio to: 1) practice slowing their resting respiratory rate to 5 to 10 breaths per minute for at least 15 minutes/day at home using a portable guided-breathing device; or 2) use an identical-appearing control device that plays non-rhythmic music while monitoring their spontaneous breathing pattern. Women will be told that they are enrolling in a study of two types of relaxation therapy for OAB, and that we do not know which, if either, is effective in treating OAB. All women will also receive a usual care pamphlet providing basic

information about pelvic floor muscle exercises, and other traditional self-management strategies for OAB.

Participants will return to the clinic at 1 week to reinforce correct use of their devices and at 6 and 12 weeks to provide outcomes data; they will also complete a mail-in packet 12 weeks after returning their devices. To address Aim 1, we will assess changes in frequency of voiding and incontinence episodes associated with at least a moderate sensation of urgency as measured by validated voiding diaries, as well as changes in frequency of other OAB symptoms and quality-of-life impact of OAB symptoms measured by both diaries and validated questionnaires. To address Aim 2, we will assess for improvement in autonomic nervous system control using several physiologic measures (heart rate variability, pre-ejection period) and explore change in autonomic control as a mechanism of treatment effects on OAB. For Aim 3, we will assess changes in anxiety-related symptoms using validated questionnaires and assess whether these mediate treatment effects on OAB.

D.2 Study Population and Eligibility Criteria

Overview: Participants will be ambulatory women who have frequent OAB symptoms, report no prior complex urologic history, are not currently using other OAB treatments, and are willing to use the breathing device.

Inclusion criteria

- 1) Women aged 21 years or older who are able to walk to the bathroom without assistance

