- 2) Report recurrent episodes of urgency (sudden or strong urges to urinate) beginning at least 3 months prior to screening
- 3) Able to record all voiding and incontinence episodes on a screening 3-day voiding diary^{29,30} and rate the severity of urgency associated with each episode using a validated urgency severity scale³¹
- 4) Document at least 9 voiding or incontinence episodes on the above 3-day voiding diary that are associated with at least moderate sensation of urgency (using the above validated urgency severity scale)³¹
- 5) Willing to refrain from initiating other treatments that may affect voiding pattern during the trial period

Exclusion criteria

- 1) Use of anticholinergic OAB medications or other medications known to affect urinary function (i.e., diuretics, tricyclic antidepressants) within 1 month of screening
- 2) Current urinary tract infection (detected via screening dipstick urinalysis or urine culture) or a history more than 3 urinary tract infections in the preceding 1 year
- 3) Prior history of lower urinary tract surgery, pelvic cancer, or pelvic irradiation; or other pelvic or abdominal surgery within 6 months of screening
- 4) History of interstitial cystitis, fistula in the bladder or rectum, or congenital or childhood defect leading to chronic urinary incontinence, retention, or other chronic urinary symptoms

- 5) Known history of major neurologic conditions likely to have major or permanent effects on bladder function such as stroke, multiple sclerosis, spinal cord injury, or Parkinson's disease
- 6) Use of bladder botulinum injections, electrostimulation, or other invasive therapies for OAB or incontinence within 3 months of screening
- 7) Formal pelvic floor rehabilitation or other formal behavioral therapy for bladder symptoms involving a physical therapist or other certified practitioner within 3 months of screening
- 8) Started, stopped, or changed dosage of a psychoactive medication likely to affect anxiety (SSRIs/SNRIs, tricyclics) within 3 months of screening, or plans to start, stop, or change dosage during the trial
- 9) Resting blood pressure (average of 2 measures) less than 100/60 at screening (women with baseline low blood pressure may theoretically be at increased risk of hypotension with use of RESPeRATE)
- 10) Resting breathing rate already below 10 breaths/minute before treatment (as measured during run-in)

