Participants in this trial will use RESPeRATE, a small, commercially-available guided-breathing device manufactured by Intercure, Ltd. that is currently FDA-approved for treatment of mild hypertension. The

RESPeRATE device includes a belt-type respiration sensor that is placed around the user's chest over the clothing, along with a small computerized box that generates musical tones transmitted through attached earphones. Using the belt-type sensor, the device first senses the user's spontaneous respiratory rate, while playing quiet, relaxing, non-rhythmic music. The device then begins to play distinct musical tones to guide the user in slowing her respiratory rate and prolong her expiratory phase. In the proposed clinical trial, women will be

randomized to receive either: 1) a standard, active RESPeRATE device that guides the user in breathing at a rate slower than 10 BPM, or 2) an identical-appearing control device that does not pace respiration but continues to monitor spontaneous breathing rate while playing relaxing, non-rhythmic music. Participants in both groups will be instructed to use their devices for at least 15 minutes per day for 12 weeks.

D.4.2 Active intervention

Participants who are randomized to the active intervention group will receive an active RESPeRATE device at the baseline visit that is programmed to pace respiration at less than 10 BPM (identical to current FDA-approved use of the device for treatment of hypertension). After reading the device instructions, the participant will be asked to place the belt-like elastic strap respiratory sensor around the upper chest over clothing under the axillae and above the breasts. The participant will then place the headphones on the ears and breathe normally until the device recognizes her normal respiratory rate.

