- A. Heart rate variability: Heart rate variability (i.e., fluctuation in instantaneous heart rate that results from autonomic influences on the sinus node) is a well-established measure of overall autonomic balance, and a validated marker of risk for adverse outcomes of other chronic conditions associated with autonomic dysfunction such as coronary disease and heart failure⁴¹. In particular, the high frequency (0.12-0.40 Hz) component of heart rate variability provides a reliable marker of *parasympathetic* autonomic activity, based on autonomic blockade studies showing that heart rate variability in the high frequency range is influenced by vagal but not sympathetic influences on the heart⁴²⁻⁴⁴. Measurements will be obtained at baseline and 12 weeks for visits at the [name] site only using a Biopac MP150 monitoring system (Santa Barbara, CA), according to protocols established by the North American Society of Pacing and Electrophysiology⁴⁵. Specifically, two electrocardiograph (ECG) electrodes will be attached to participants' torso/chest, and a 20-minute continuous ECG recording will then be taken with the participant in the seated position. Prior to measurement, women will be queried about any history of cardiac arrhythmias that could influence heart rate variability interpretation. To minimize diurnal variation, recordings will be obtained in the same 2-hour time of day at both visits. Women will sit in a quiet, ambient-temperature room, and will also be asked to abstain from tobacco or alcohol for 24 hours prior to recording. For 10 minutes during recording, they will also be asked to perform two computer-based stress tasks designed to assess vagal reactivity and sympathetic nervous system activity. Data will be analyzed using Mindware software (Gahanna, OH), which will calculate multiple time domain heart rate variability parameters (e.g., mean heart rate, standard deviation of N-N interval, square root of mean squared difference of successive N-N

intervals), as well as frequency domain heart rate variability parameters reflecting the distribution of heart rate variability over different frequencies (e.g., high frequency (0.12-0.40 Hz), low frequency (0.04-0.12 Hz), and low frequency/high frequency ratio).

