Secondary outcomes include 12-week change in autonomic control as assessed by high frequency heart rate variability (RSA) and pre-ejection period (PEP), as the purest available measures of parasympathetic and sympathetic function. Treatment effects on each of these measures will initially be estimated using ANCOVA models, first to examine effects on resting parameters, followed by examination of effects on rest-to-stress change (i.e., reactivity) while adjusting for baseline levels of each parameter. Treatment effects will again be examined by intention to treat, according to treatment assignment, and without regard to adherence. Autonomic parameters will be transformed as necessary if their distributions appear significantly skewed. We will then assess for mediation of treatment effects on OAB symptoms by improvement in autonomic control using structural equation modeling. This will involve fitting an initial model that includes both autonomic parameters and anxiety symptoms (as described below in the statistical plan for Aim 2), then extracting coefficients for each of the hypothesized mediating pathways.

Aim 3: To determine whether this slow-breathing intervention can improve anxiety-related symptoms in women with OAB, and explore changes in anxiety as a mediator of treatment effects on OAB symptoms.

Expected outcomes: Women with OAB randomized to practice slow-breathing exercises will report significant improvement in anxiety-related symptoms (as measured by validated questionnaires), and treatment effects on OAB symptoms will be at least partly mediated by improvement in anxiety.

Additional outcomes will include change in anxiety symptoms from baseline to 12 weeks, measured by scores on the validated STAI, HADS, PSS, and BDI questionnaires. Intervention effects will again be estimated using ANCOVA, adjusted for baseline questionnaire scores. Anxiety symptom outcomes will be transformed as necessary if their distributions appear skewed. To assess for mediation of treatment effects on the primary outcome by change in anxiety symptom scores (as well as autonomic parameters as noted in the statistical plan for Aim 2), we will use structural equation modeling as outlined above).

D.10.2 Sample size estimates

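### The HF band behind the Aim 2 parasympathetic outcome starts at 7.2 breaths/min, inside the range trained in the active arm, and the plan neither sets nor uses breathing rate for the recording

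*Combined protocol and SAP*

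**What the plan says.** - **Measure (D.5.2 A).** The protocol states that "the high frequency (0.12-0.40 Hz) component of heart rate variability provides a reliable marker of" parasympathetic activity, on the ground that this range reflects vagal and not sympathetic influence. It lists the frequency-domain parameters as "high frequency (0.12-0.40 Hz), low frequency (0.04-0.12 Hz), and low frequency/high frequency ratio". The ECG is a 20-minute seated recording in a quiet room at baseline and 12 weeks, at one site, with 10 minutes given to two stress tasks. Time of day, tobacco, alcohol and arrhythmia history are addressed. Breathing is not.
- **Intervention (D.1, D.4.2).** The active arm is to "practice slowing their resting respiratory rate to 5 to 10 breaths per minute for at least 15 minutes/day at home", sitting quietly, with a device "programmed to pace respiration at less than 10 BPM". The control device does not pace breathing.
- **Entry (D.2, exclusion 10).** Women whose resting rate in the run-in is already below 10 breaths/min are excluded.
- **Analysis (D.10.1, Aim 2).** The outcomes are "high frequency heart rate variability (RSA) and pre-ejection period (PEP), as the purest available measures of parasympathetic and sympathetic function". ANCOVA is applied to resting values and then to rest-to-stress change. The autonomic measures also enter a structural equation model as mediators. No respiratory term or rule for out-of-band breathing is given.
- **Respiratory rate (D.5.6, D.6.4, D.6.8).** It is measured at visits but not linked to the HRV recording or its analysis.

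**The concern.** As general physiology, the respiratory component of heart rate variability appears at the breathing frequency; the protocol's label RSA (respiratory sinus arrhythmia) for HF-HRV points the same way. If breathing slows past the lower band limit, that component is counted as LF even when vagal modulation is unchanged. HF then falls and LF/HF rises.

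Only one arm is trained to slow its breathing while seated and quiet, and women enter at 10 breaths/min or more, inside the HF band. A drop below the limit would therefore arise after randomisation and mainly in the active arm, so the measurement error would depend on treatment. Three results are exposed:

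- **Resting HF-HRV** would be understated in the active arm, against the Aim 2 hypothesis.
- **Rest-to-stress change** would be distorted. A woman who rests below the limit and breathes faster during a task gains HF power as she enters the task, which can hide the vagal withdrawal that one task is meant to provoke (D.8.1 F). The plan does not say which direction of reactivity counts as improvement.
- **The mediation path** through HF-HRV would be weakened or reversed if the women who slow most appear to improve least.

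Baseline may also be exposed. D.6.4 describes the HRV measurement after randomisation and device instruction, though it does not clearly fix that order.

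**Working it through.** The plan gives no figure of its own to reproduce here, so the check starts with a unit conversion.

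**1. Bands in breaths/min** (Hz x 60; limits from D.5.2 A)
- LF: 0.04 x 60 = 2.4 to 0.12 x 60 = 7.2
- HF: 0.12 x 60 = 7.2 to 0.40 x 60 = 24

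**2. Trained range in Hz** (5 to 10 breaths/min, Specific Aims and D.1)
- 5/60 = 0.083 Hz and 10/60 = 0.167 Hz
- Part below the HF limit: 5 to 7.2, or (7.2 - 5)/(10 - 5) = 44% of the interval's width. The other 56% stays in HF.

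**3. How slow breathing must be to matter.** A simulated heart-rate oscillation of constant amplitude was placed at the breathing frequency, with an assumed 8% rate jitter over 10 minutes. Its power was summed over the plan's two bands.

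| Breaths/min | HF share of power |
|---|---|
| 14 | 1.00 |
| 10 | 1.00 |
| 8 | 0.96 |
| 7.2 | 0.47 |
| 7 | 0.27 |
| 6 | 0.01 |
| 5 | 0.00 |

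The loss is steep but begins only close to the limit. Breathing at 8 to 10 is read almost correctly.

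**4. How many women might be affected.** The documents give no breathing rate during the recording. Assume the active-arm rate at 12 weeks is normal with mean m and SD s. The share below 7.2 is then Phi((7.2 - m)/s). For example, m = 10 and s = 2 give Phi(-1.4) = 8.1%.

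| Assumed arm mean | s = 1.5 | s = 2 | s = 3 |
|---|---|---|---|
| 14 | 0.0% | 0.0% | 1.2% |
| 12 | 0.1% | 0.8% | 5.5% |
| 10 | 3.1% | 8.1% | 17.5% |
| 8 | 29.7% | 34.5% | 39.5% |

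Section C calls 14 breaths/min a normal resting rate, so the first row corresponds to no carry-over of training. The last row needs strong carry-over into unguided breathing.

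**The case against.** The strongest objection is that the 5 to 10 target belongs to home practice with the device. The HRV measurement is described as resting, and nothing says the device is used during it. The problem needs unguided breathing near or below about 7 breaths/min in clinic, which the documents neither report nor predict. This stands, and it makes the point conditional.

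Three stronger readings are tempting and are not supported:

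- **Successful slow breathing in general would look like vagal loss.** The device counts time under 10 breaths/min as effective (D.4.2, D.5.4), and breathing at 8 to 10 stays in the HF band.
- **44% of women or recordings are affected.** That figure is only the width of an interval.
- **A definite shift of the arm mean can be stated.** Taking 10-20% of women affected and a loss of 1.5 SD each gives 0.10 x 1.5 = 0.15 to 0.20 x 1.5 = 0.30 SD, which looks large beside the 0.5 SD in D.10.2. Neither factor comes from the documents, and the share could be close to zero.

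There is also partial mitigation. Time-domain HRV is already calculated, respiratory rate is taken at the 12-week visit, and pre-ejection period is a separate autonomic outcome. The recording follows cited society standards that are not available here and may cover breathing conditions. None of this is connected to the HF analysis in the plan as written.

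Finally, a band that follows each woman's breathing has its own weakness. It would reach into the plan's LF range, for which D.5.2 A makes no vagal-only claim, and it could differ systematically between arms.

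**Conclusion.** The point holds as a conditional gap in specification. The band limits and the trained range overlap imperfectly by the protocol's own figures, and no breathing condition, out-of-band rule or use of respiratory rate protects the HF-HRV analysis. Whether this produces bias depends on one unknown, the active arm's breathing rate during the 12-week recording. On the assumed distributions, the share below 7.2 breaths/min runs from about 0-1% (mean 14) to 30-40% (mean 8), so the consequence runs from negligible to material. A reader might infer that the Aim 2 result is bound to be biased; the documents do not show that.

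The reach is limited to a secondary outcome measured at one site and an exploratory mediation analysis. The primary diary outcome is not touched. The case for acting now is that, without a rule, a null or negative HF result could not be told apart from slow breathing, and a band changed after the data are seen would look data-driven.

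**What to change.** 1. Keep fixed-band HF (0.12-0.40 Hz) as the main parasympathetic measure.
2. At baseline and 12 weeks, instruct both arms to breathe spontaneously and not to practise the technique during the resting segment. This does not remove a lasting change in resting breathing, so the next steps are still needed.
3. Derive breathing frequency from the impedance signal recorded with the ECG (D.5.2 B) where its quality allows; otherwise use the respiratory rate measured at the visit. The plan currently uses impedance only for pre-ejection period, so quality should be checked first.
4. Report by arm and visit the number of recordings with breathing outside 0.12-0.40 Hz.
5. Pre-specify a sensitivity analysis with a respiration-adapted band. Give the root mean square of successive N-N differences as supportive only, since it too may depend on breathing.
6. State that HF and LF/HF will not be interpreted as vagal change in out-of-band recordings.

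The cost is some signal processing, a short standard instruction and a few lines of analysis plan, with no new equipment or visit. The downside is that the adapted band overlaps the plan's LF range and may differ by arm, which is why it belongs in a sensitivity analysis.

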Because of the behavioral nature of the treatment interventions, study participants cannot be fully blinded to treatment assignment. However, several steps will be taken to minimize possible bias arising from lack of blinding. Participants will be told that they are participating in a study of two different types of relaxation therapy, slow-paced respiration versus music-listening, for treatment of overactive bladder symptoms. They will be told that the investigators do not yet know whether one form of therapy is more effective than the other.

in controlling bladder symptoms (which is true). All participant materials will be developed to avoid giving participants the impression that slow-paced respiration is believed to be more effective than relaxing music-listening in controlling overactive bladder. Information listed on clinicaltrials.gov and other public registries will also avoid implying that one form of therapy is more effective than the other.

When interacting with participants, study staff will refer to the RESPeRATE device as the “CURE study relaxation device” rather than a “RESPeRATE device,” since the control device will be used differently from a standard, commercially-available RESPeRATE device. Participant-oriented study materials will also refer to the device as a “relaxation device” and avoid referring to either RESPeRATE or Intercure Ltd.

The primary outcome, change in frequency of voiding or incontinence episodes associated with at least moderate urgency, will be assessed using 3-day voiding diaries, which are likely to be more resistant to bias than other types of self-report measures. Although clinical staff responsible for conducting study visits will not be blinded to treatment assignment (so that they can assist participants with problems using their RESPeRATE devices), the study investigators will be blinded to treatment assignment. A subset of voiding diaries from both the [name] and [name] sites will be reviewed by a blinded analyst for quality control.

D.4.6 Overactive bladder self-management pamphlet

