home practice for at least 12 minutes on each of at least 6 days, the voiding diary is completed correctly on at least 3 days, and the diary reveals an average of at least 3 voiding or incontinence episodes per day associated with at least moderate urgency, and the participant meets other eligibility criteria and agrees to enroll in the study, she will be eligible for randomization to a regular active or control RESPeRATE device. Immediately following proof of eligibility, the study coordinator will randomize the participant, using the next sequential randomization envelope.

Following randomization, instruction in use of the active or control RESPeRATE device will be reviewed, and the participant will be asked to use the device for at least 15 minutes per day at home. The participant will be given the study phone number and instructed to call study staff for any questions or problems with the devices. Participants will be given a pamphlet providing brief information about usual care behavioral self-management of overactive bladder symptoms. Participants will be reminded not to take any medications known to affect overactive bladder symptoms during the treatment period.

Participants will also undergo non-invasive measurement of resting heart rate variability and pre-ejection period using the BIOPAC MP150 monitoring device at this visit (if they are randomized). They will complete questionnaires assessing condition-specific quality of life and anxiety and perceived stress symptoms.

D.6.5 Follow-up Visit (1 week)

After one week of treatment, participants will return to the clinic for early follow-up, bringing their RESPeRATE active or control devices. Downloaded RESPeRATE device data will be securely transferred to the study database. The study coordinator will review adherence with use of the active or control device, assess for side effects of treatment, and answer any questions. For safety monitoring, blood pressure, heart rate, and respiratory rate will be reassessed by study staff. Adverse events will be recorded on standardized forms. Each participant will also be given a new, blank voiding diary to complete for 3 days before her 6-week visit.

D.6.6 Follow-up Visit (6 weeks)

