Appendix A: Summary of Measures & Procedures at Study Visits

Measures	Telephone Screening	Screening Clinic Visit	Run-in period*	Baseline Clinic Visit	1week Clinic Visit	3-week Phone Call	6-Week Clinic Visit	9-week Phone Call	12-week Final Visit	24-week Mail-in
Brief telephone screening interview	X									
Informed consent and HIPAA documentation		X								
Demographic, medical & surgical history		X								
Review of current and past medications		X							X	
Alcohol and tobacco use questionnaires		X								
Height and weight measurement		X							X	
Heart rate and blood pressure measurement		X		X	X		X		X	
RESPeRATE control device run-in			X							
Review of 3-day voiding diary				X			X		X	X
Overactive Bladder Questionnaire				X			X		X	X
Urgency Severity & Impact Scale				X			X		X	X
Urogenital Distress Inventory				X			X		X	X
Spielberg State-Trait Anxiety Inventory				X			X		X	X
Hospital Anxiety and Depression Scale				X			X		X	X
Perceived Stress Scale				X			X		X	X
Center for Epidemiologic Studies Depression				X			X		X	X
Randomize to active versus control device				X						
Self-management OAB pamphlet distributed				X						
Heart rate variability measurements				X					X	
Impedance cardiography measurements				X					X	
3-day wrist actigraphy				X					X	
Sleep diary (to accompany actigraphy)				X					X	
Adverse events assessment				X	X	X	X	X	X	
Downloading of RESPeRATE device data				X	X		X		X	
Satisfaction questionnaire									X	

REFERENCES CITED

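### The autonomic baseline is taken after the randomization envelope is opened, and nothing places the baseline questionnaires before it, yet both serve as baseline covariates in ANCOVA

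*Combined protocol and SAP*

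**What the plan says.** Section D.6.4 describes one visit. Run-in data, diary and blood pressure are checked, and then: "Immediately following proof of eligibility, the study coordinator will randomize the participant, using the next sequential randomization envelope". The next paragraph begins "Following randomization, instruction in use of the active or control RESPeRATE device will be reviewed" and goes on to the pamphlet. The paragraph after that provides for "measurement of resting heart rate variability and pre-ejection period using the BIOPAC MP150 monitoring device at this visit (if they are randomized", and ends: "They will complete questionnaires assessing condition-specific quality of life and anxiety and perceived stress symptoms".

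Three other places bear on this:

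- **Device and blinding.** Under D.4.2 a woman in the active arm "will receive an active RESPeRATE device at the baseline visit". D.4.5 accepts that "study participants cannot be fully blinded to treatment assignment".
- **Appendix A.** Seven questionnaires (OAB-Q, USIQ, UDI-6, STAI, HADS, PSS, CES-D) stand above the row "Randomize to active versus control device". Heart rate variability and impedance cardiography stand below it.
- **Analysis (D.10.1).** The autonomic outcomes of Aim 2 are analysed by ANCOVA with adjustment for baseline parameter levels. For the anxiety outcomes of Aim 3: "Intervention effects will again be estimated using ANCOVA, adjusted for baseline questionnaire scores". The Aim 1 symptom-bother and impact questionnaires are also analysed by ANCOVA. The autonomic and anxiety measures then enter a structural equation model for mediation.

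The diary that supplies the baseline for the primary outcome is kept during the run-in (D.6.3), before assignment.

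**The concern.** Baseline adjustment in a randomized comparison is unbiased because the covariate is fixed before assignment and so cannot depend on it. A measurement taken after the envelope is opened loses that guarantee. Here the woman may know which therapy she has drawn and has her device at the visit. Anxiety, stress and resting autonomic tone could respond to that news or to a first try of the device. If they respond differently by arm, ANCOVA treats part of a treatment effect, or of a reaction to assignment, as a pre-existing difference and removes it. The same shift passes into any change score used as a mediator. A true pre-randomization value cannot be recovered afterwards.

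**Working it through.** **1. Order of events.**

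- *Autonomic recording versus envelope.* The recording is conditional on being randomized, and randomization follows eligibility immediately. The condition can be applied only once randomization has happened, so the recording comes after the envelope.
- *Autonomic recording versus device teaching.* No sentence fixes this. Teaching is described first, but only as narrative.
- *Questionnaires versus envelope.* No sentence fixes this. D.6.4 describes them last; Appendix A lists them above the randomization row. Appendix A is not chronological: actigraphy and the sleep diary, done in the run-in, sit below that row. It cannot settle the order either way.

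No section requires any of these baselines to precede assignment.

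**2. The plan's own figure for secondary outcomes.** D.10.2 gives 80% power, two-sided 5%, for 0.5 SD, with correlation rho of 0.4 to 0.8. With 80 per arm and 15% loss, 80 × 0.85 = 68 per arm. The detectable difference is (1.960 + 0.842) × √(1 − rho²) × √(2/68):

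- no adjustment: 0.48 SD
- rho = 0.4: 0.44 SD
- rho = 0.6: 0.38 SD
- rho = 0.8: 0.29 SD

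So 0.5 SD is attainable if all sites contribute. Heart rate variability and pre-ejection period are measured at one site only, so 68 per arm is an upper limit for them.

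**3. Bias formula.** The ANCOVA estimate is the follow-up difference between arms minus b times the baseline difference, where b is the within-arm slope. With equal SDs at both times, b = rho. If assignment adds s SD to the recorded baseline in one arm, the expected estimate is the true effect minus rho × s. This is the same whether the outcome is entered as follow-up value or as change.

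**4. Size.** The documents give no s, so the columns below are assumptions. Entries are rho × s in SD, with the percentage of 0.5 SD.

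| rho | s = 0.10 | s = 0.20 | s = 0.25 |
|---|---|---|---|
| 0.4 | 0.04 (8%) | 0.08 (16%) | 0.10 (20%) |
| 0.6 | 0.06 (12%) | 0.12 (24%) | 0.15 (30%) |
| 0.8 | 0.08 (16%) | 0.16 (32%) | 0.20 (40%) |

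A simulation of 5,000 trials with 68 per arm, rho = 0.6, s = 0.2 and a true effect of 0.5 SD gave a mean estimate of 0.381. The formula gives 0.5 − 0.6 × 0.2 = 0.380.

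**5. Consequences at s = 0.2, 68 per arm.**

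- With a true 0.5 SD effect and a shift towards benefit, power falls from 89% to 76% (rho 0.4), from 95% to 79% (rho 0.6) and from 99.8% to 91% (rho 0.8).
- With no true effect at 12 weeks, two-sided type I error rises from 5% to 8%, 14% and 34% respectively.
- A shift away from benefit inflates the estimated effect by the same rho × s.

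**6. What a sensitivity analysis must avoid.** Comparing 12-week values without the baseline removes this bias; the detectable difference becomes 0.48 SD. An unadjusted comparison of change scores does not help: its bias is the full −s.

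**The case against.** The strongest reply is that D.6.4 is loosely written, not wrongly ordered. Its third paragraph is a list of things done at the visit, and the parenthesis may mean only that women found ineligible are spared the recording. That is a fair account of the likely intent. It does not remove the problem for the autonomic recording, because the literal condition puts it after the envelope and no other section says otherwise.

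Several stronger readings are tempting, and the documents do not support them.

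- *Both sets of baselines follow device teaching.* A reader might infer this from paragraph order, but no sentence says so, and Appendix A lists the questionnaires above randomization.
- *Active-arm women have just practised slow breathing when recorded.* D.6.4 says only that instruction is reviewed. D.4.2 describes how the device is fitted and works, not a completed session before the recording.
- *Pacing must distort the high-frequency band.* Five to 10 breaths per minute is 5/60 = 0.083 to 10/60 = 0.167 Hz, which straddles the 0.12 Hz band edge (7.2 breaths per minute). That matters only for breathing during the recording. D.5.2 mentions no device use then, and the argument does not apply to pre-ejection period.
- *Every questionnaire is equally exposed.* The STAI trait component, the PSS (past month) and the PSQI (one week) are not built to register a reaction of minutes, and women are told that neither therapy is known to be better.
- *Only the diary is safe.* Baseline actigraphy is also collected in the run-in.

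It is also fair to say that an s of 0.25 would be half of what 12 weeks of treatment is powered to detect. The upper end of the range is illustrative.

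**Conclusion.** As written, the autonomic baseline for Aim 2 is post-randomization, and the plan does not ensure that the questionnaire baselines for Aim 3 and for part of Aim 1 are pre-randomization. Whether treatment or its disclosure actually moves these values is possible but not shown. The resulting bias is 0.04 to 0.20 SD if s lies between 0.10 and 0.25 and rho between 0.4 and 0.8. It is zero if s is zero, and its sign is unknown in advance. These figures assume a constant additive shift in one arm and equal SDs at the two times. For heart rate variability and pre-ejection period the power and type I error figures are only indicative, because the number of women at the one measuring site is not given; the bias itself does not depend on that number. The mediation models inherit the problem, but its size there cannot be worked out because the plan does not say how change is coded. The primary outcome and the planned sample size are untouched. This should be fixed; confidence is moderate because part of the visit order is unstated.

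**What to change.** Rewrite the order in D.6.4: confirm diary, run-in and blood pressure eligibility; complete all baseline questionnaires and the BIOPAC recording; only then open the envelope and teach the assigned device. Replace the parenthetical condition on the recording with *if eligible, before randomization*. Align Appendix A, either by moving the heart rate variability and impedance rows above the randomization row or by stating that rows are not in time order.

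The cost is one protocol paragraph and a visit checklist. Planned procedures and sample size stay the same. The only loss is an occasional recording in an eligible woman who is then not randomized.

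For any women already enrolled, document the time of each baseline measurement relative to randomization and to first device use. Report a sensitivity analysis that compares 12-week values without the post-randomization covariate, not change scores, and accept its lower precision.
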